12.6	DATA SECURITY AND CONFIDENTIALITY	18
12.7	DATA QUALITY ASSURANCE	18
12.8	DATA CLARIFICATION PROCESS	18
12.9	RECORDS RETENTION.....	18
13	STUDY MONITORING, AUDITING, AND INSPECTING	18
13.1	STUDY MONITORING PLAN.....	18
13.2	AUDITING AND INSPECTING	18
14	ETHICAL CONSIDERATIONS.....	19
15	STUDY FINANCES.....	19
15.1	FUNDING SOURCE	19
15.2	CONFLICT OF INTEREST.....	19
15.3	SUBJECT STIPENDS OR PAYMENTS	19
16	PUBLICATION PLAN	19
17	REFERENCES.....	20
18	LIST OF IN-TEXT TABLES.....	20
18.1	SCHEDULE OF EVENTS	20
18.2	INTRAOPERATIVE DATA	21
19	LIST OF IN-TEXT FIGURES.....	24
19.1	TETRAGRAPH.....	24

1 Protocol Approval Form

Protocol Number: 20-001771

Study Name: Correlation between cardiac output and recovery time after reversal of rocuronium-induced blockade with sugammadex

This protocol has been reviewed and approved by the following:

J. [name]
Principal Investigator

17/Aug/2022

Date

2 List of Abbreviations

AE	Adverse Event/Adverse Experience
AMG	Acceleromyography
CE	Conformite Europeene
CFR	Code of Federal Regulations
cMAPs	Compound Muscle Action Potentials
CO	Cardiac Output
CRF	Case Report Form
CTSA	Center for Translational Science Activities
DSMB	Data and Safety Monitoring Board
EHR	Electronic Health Record
EMG	Electromyography
FDA	Food and Drug Administration
GCP	Good Clinical Practice
HIPAA	Health Insurance Portability and Accountability Act
IB	Investigator's Brochure
ICU	Intensive Care Unit
IRB	Institutional Review Board
KMG	Kinemyography
MMG	Mechanomyography
NMBA	Neuromuscular Blocking Agent
Non-UPIRTSO	Non-Unanticipated Problems Involving Risk to Subjects or Others
PACU	Post Anesthesia Care Unit
PHI	Protected Health Information
PI	Principal Investigator
PTC	Post-tetanic Potentiation
SAE	Serious Adverse Event/Serious Adverse Experience
SGX	Sugammadex
SOP	Standard Operating Procedure
TOF	Train-of-four
TOFC	Train-of-four count
TOFR	Train-of-four ratio
UPIRTSO	Unanticipated Problems Involving Risk to Subjects or Others
VNRS	Verbal Numeric Rating Scale

3 Study Summary

Title	Correlation between cardiac output and recovery time after reversal of rocuronium-induced blockade with sugammadex
Running Title	CO and Sugammadex
Phase	N/A
Methodology	Open-Label
Overall Study Duration	6 months
Subject Participation Duration	2 – 5 hours
Single or Multi-Site	Single site
Objectives	The primary aim of this study is to correlate the temporal relationship between cardiac output and clinical recovery of neuromuscular block affected by sugammadex.
Number of Subjects	50
Diagnosis and Main Inclusion Criteria	Patients undergoing elective surgery and requiring administration of rocuronium, and the use of a pulmonary artery catheter intraoperatively.
Study Device	TetraGraph
Duration of Administration	Single stimulation of ulnar nerve repeated at specific intervals as outlined in the Study Procedures (Section 9.2)

4 Introduction

This document is a protocol for a human research study. This study will be carried out in accordance with the applicable United States government regulations and Mayo Clinic research policies and procedures.

4.1 Abstract

Sugammadex has been introduced into the market as a fast-acting selective relaxant binding agent to reverse rocuronium-induced neuromuscular block. Several studies have shown that longer times are required in older patients to recover from rocuronium-induced neuromuscular block, which is likely related to age-related decreases in cardiac output. The aim of this study is to evaluate the correlation between cardiac output and speed of reversal of rocuronium-induced neuromuscular block with sugammadex in patients.

4.2 Background

Neuromuscular blocking agents (NMBAs) are a class of medications routinely used during anesthesia to facilitate endotracheal intubation (1), and improve conditions for optimal surgery (2). Routine reversal of neuromuscular blockade is very common in order to return patients' spontaneous breathing and prevent residual blockade and all the associated complications (3, 4). Sugammadex, a novel γ -cyclodextrin, is a unique neuromuscular reversal drug discovered by Anton Bom. It is the first in a new class of selective relaxant binding agents, and it was designed to rapidly reverse rocuronium-induced neuromuscular block (5, 6). Sugammadex-rocuronium interaction reduces the amount of free muscle relaxant in the plasma, reducing the level of free NMBA at the neuromuscular junction (7). Some studies have shown that longer times are required in older patients to recover from rocuronium-induced neuromuscular block (8). Suzuki et al, showed that achieving a TOFR of 0.9 was slower in older than younger patients. In addition, Yoshida et al (9), reported that in elderly patients (65 years or older), the time to reach a TOFR of 0.9 following 2 mg/kg sugammadex was dependent on the cardiac output. These studies suggested that the slower duration to reach a TOFR of 0.9 in older patients is probably attributable to their lower cardiac output. However, they had a limitation and it was the technique they used to measure the cardiac output because compared with other invasive techniques, FloTrac/Vigileo tends to underestimate the cardiac output (10).

The purpose of this study is to determine the recovery time from rocuronium-induced blockade after reversal with sugammadex as a function of cardiac output in elderly and young patients. Cardiac output measurements will be performed pulmonary artery catheterization, which is passing a catheter into the right side of the heart and the arteries leading to the lungs to monitor heart function and blood flow pressures. It is important to highlight that pulmonary artery catheter would be part of the normal care and intraoperatively proceedings. Neuromuscular monitoring will be performed using TetraGraph (Senzime AB, Uppsala, Sweden) which is a standalone EMG-based quantitative monitor that is FDA approved. EMG measures electrical activity within the muscle following peripheral nerve stimulation and is unaffected by involuntary patient motion or restricted muscle movements from surgical positioning.

4.3 Risks and Benefits

- The benefits of using neuromuscular blockade monitoring devices:
Early detection of optimal time for tracheal intubation; optimal management of intraoperative depth of neuromuscular block to facilitate surgical procedures; determination of appropriate time and dose of sugammadex reversal; and detection of residual neuromuscular blockade
- The risks of using neuromuscular blockade monitoring devices:
Slight discomfort when electrical stimulation is administered in awake volunteers; however, our patients will be anesthetized, rendering this risk as extremely minor.

5 Study Objectives

Primary Objective

To determine the recovery time from rocuronium-induced blockade after reversal with sugammadex as a function of cardiac output.

Secondary Objective

To determine the correlation between the speed of recovery from NMBA with sugammadex and age.

6 Study Design

6.1 General Description

This single center, prospective, observational study will involve 50 patients undergoing surgical procedure that involved administration of neuromuscular blockade agents intraoperatively.

6.2 Number of Subjects

Fifty

6.3 Duration of Participation

2-5 hours, depending on duration of surgery

6.4 Primary Study Endpoints

The primary endpoint of the study will be to examine the correlation between cardiac output and the time of recovery after reversal with sugammadex as measured by TOFR ≥ 0.9 .

6.5 Secondary Study Endpoints

The secondary endpoint is the incidence of postoperative residual weakness at the time of extubation.

6.6 Identification of Source Data

The study data points will be recorded on the developed Case Report Forms (CRFs) by the study team members. In addition to the data collected intraoperatively, several intraoperative characteristics will also be extracted from the medical record ([Table 18.2](#)). These will include type and total dose of NMBA used, time and dose of last NMBA administration, time and dose of specific reversal agent administration, time of tracheal extubation, and TOF ratio at the time of extubation (if available).

7 Subject Selection Enrollment and Withdrawal

7.1 Inclusion Criteria

- Age > or = 18 years old
- Patients willing to participate and provide an informed consent
- Patients undergoing an elective surgical procedure requiring administration of rocuronium, and the use of a pulmonary artery catheter intraoperatively.

7.2 Exclusion Criteria

- Patients with unilateral disorders, such as stroke, carpal tunnel syndrome, broken wrist with nerve damage, Dupuytren contracture
- Patients with systemic neuromuscular diseases such as myasthenia gravis
- Patients with significant organ dysfunction that can significantly affect pharmacokinetics of neuromuscular blocking and reversal agents, i.e., severe renal impairment or end-stage liver disease.
- Patients having surgery that would involve prepping the arm or leg into the sterile field

7.3 Subject Recruitment, Enrollment and Screening

On a daily basis, there are over 20 elective surgical cases performed at Mayo Clinic in Florida and thus no difficulties in accrual are anticipated based on historical volumes. We will target at least 3 participants per week to complete this study. The initial accrual period will last at least 3 months followed by interim analysis and additional time for accrual will be determined to meet the target. Patients will be provided with a Research Participant Consent and Privacy Authorization Form describing the study devices, protocol, inclusion and exclusion criteria, as well as risks and benefits of participation.

7.4 Early Withdrawal of Subjects

7.4.1 When and How to Withdraw Subjects

Patients are free to withdraw at any time and for whatever reason. If patient withdraws consent prior to arrival to operating room, the study data will not be collected. If patient withdraws consent after study data was already completed, the participant will need to provide instructions to the study team to remove his/her data from the data set. Pre-specified reasons for discontinuing include, but are not limited to, the following:

- Patient Request: Patient decided that he/she did not want to continue (for any reason)
- Adverse Event: Patient experienced a related or unrelated event that would interfere with the study objectives/evaluation
- Inclusion/Exclusion Discrepancy/Violation: Patient should not have been enrolled
- Other: Any other reason

7.4.2 Data Collection and Follow-up for Withdrawn Subjects

If a Participant withdraws from the study, no additional attempts will be made to contact the Participant.

8 Study Device

8.1 Description

TetraGraph device is a FDA approved neuromuscular transmission monitor capable of measuring the depth of neuromuscular block in anesthetized patients who received neuromuscular blocking agents. TetraGraph uses EMG to measure the muscle action potentials that are generated in response to electrical neurostimulation via skin (ECG) electrodes.

TetraGraph data is recorded on the monitor's built-in SD card, and all intraoperative data will be recorded and later downloaded for purposes of analysis. The recorded data do not contain PHI, only the date/time of recording, and any additional intraoperative interventions, such as the time of NMBA dose administration, time of antidote administration, time of extubation, etc. These events are flagged in the monitor's integrated SD card recordings.

Cardiac Output will be measured continuously (as per standard of care) through pulmonary artery catheter, which is the passing of a thin tube into the right side of the heart and arteries leading to the lungs. This catheter will be used as part of the standardized management during the surgical procedure.

8.2 Method for Assigning Subjects to Treatment Groups

This is a single-blinded investigation and all study participants are assigned to both standard of care and investigational device use in the operating room.

8.3 Masking/Blinding of Study

This is an open-label pilot investigation. Masking and blinding procedures are not applicable.

9 Study Procedures

9.1 Visit 1 (Screening and Enrollment up to the day of surgery)

- Review of medical record
- Informed Consent - Patients will be identified during their preoperative appointment and introduced to a study; they will be provided with a copy of the consent document and information about the study. The consenting will take place after additional discussion on the day of surgery.

9.2 Visit 2 (Treatment – day of surgery)

- Elective surgical procedure as per standard of care
- Anesthetic management will be at the discretion of the attending anesthesiologist as per standard of care practice.
- Prior to induction of anesthesia, Tetragraph electrodes will be placed over the ulnar nerve and the thumb and/or pinky finger to measure the response of adductor digit minimi nerve (location of Tetragraph will be at a discretion of the anesthesiologist).
- Following induction of anesthesia but prior to NMBA administration, baseline values will be recorded after calibration.
- Cardiac output will be measured continuously through the pulmonary artery catheter and the values will be obtained from EHR.
- Near the conclusion of the operation but prior to the reversal of NMBA, a set of measurements will be taken
- After sugammadex administration, measurements will be taken every 20 seconds until consecutive measurements demonstrate a TOFR ≥ 0.9 (adequate recovery)
- Each neurostimulation with the TetraGraph will be conducted simultaneously with one observer.
- Time to recovery following SGX (TOFR ≥ 0.9) will be documented as well as time to extubation.
- Following measurements obtained the device will be removed and the patient will proceed along the standard recovery pathway.

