18.2 Intraoperative Data

Study ID:	Date of Surgery (dd / mm / yyyy):		Examiner's Initials:
Wrist circumference (right):	Wrist circumference (left):		
Age (yrs):	Weight (kg):	Height (cm):	BMI:
Muscle relaxant name:			
Muscle relaxant total dose (mg):			
Time of first muscle relaxant dose (mm : hh):		: am / pm	
Time of last muscle relaxant dose (mm : hh):		: am / pm	
Sugammadex dose (mg):			
Time of Sugammadex administration (mm : hh):		: am / pm	

Time of extubation:	:	am / pm
---------------------	---	---------

TetraGraph (TG)

Arm tested: dominant / non-dominant

	Time	TOFC # 1	TOFC # 2	TOFC # 3	CO
		TOFR # 1	TOFR # 2	TOFR # 3	
Calibrated baseline and supramax current					
TOFC=0 (after initial NMBA dose)					
pre-SGX					
+20 sec			N/A	N/A	
+40 sec			N/A	N/A	
+60 sec			N/A	N/A	
+80 sec			N/A	N/A	
+100 sec			N/A	N/A	
+120 sec			N/A	N/A	
+140 sec			N/A	N/A	
+160 sec			N/A	N/A	

+180 sec			N/A	N/A	
+200 sec			N/A	N/A	
+220 sec			N/A	N/A	
+240 sec			N/A	N/A	
+260 sec			N/A	N/A	
+280 sec			N/A	N/A	
+300 sec			N/A	N/A	
Extubation			N/A	N/A	
Time to recovery following SGX (TOFR ≥ 0.9) (two consecutive measurements)					

19 List of In-Text Figures

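### Section 9.2 does not fix the muscle at which recovery is read and no listed data source names it, so recovery times from different muscles may be pooled with no documented way to check

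*Combined protocol and SAP*

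**What the plan says.** Section 9.2 of the protocol states that "Tetragraph electrodes will be placed over the ulnar nerve and the thumb and/or pinky finger to measure the response of adductor digit minimi nerve". The same bullet, read from the second digit on, gives the discretion over site: "pinky finger to measure the response of adductor digit minimi nerve (location of Tetragraph will be at a discretion of the anesthesiologist". No rule guides the choice.

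Section 6.4 defines the primary endpoint through "the time of recovery after reversal with sugammadex as measured by TOFR ≥ 0.9" and names no muscle. Section 10.2 correlates that time with cardiac output and with age, and regresses it on either, with no term, stratum or sensitivity analysis for site.

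Three places describe what is captured:

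- Form 18.2 has the item "Arm tested: dominant / non-dominant" and wrist circumference on both sides. It has no field for muscle, digit or electrode position. It holds one TetraGraph series and one row for time to recovery.
- Section 8.1 says of the device file: "The recorded data do not contain PHI, only the date/time of recording, and any additional intraoperative interventions". Its examples are drug administration times and extubation.
- Section 6.6 lists items from the medical record: "These will include type and total dose of NMBA used, time and dose of last NMBA administration", followed by reversal, extubation time and the ratio at extubation. The monitoring site is not among them.

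**The concern.** The primary outcome is the moment at which a monitored muscle crosses a threshold, read every 20 seconds. Two hand muscles need not cross it together, so the choice of muscle is part of the outcome's definition. Section 9.2 leaves that choice open, and the target it names does not close it. The term used is called a nerve, whereas section 8.1 says the device measures muscle action potentials. It also follows a phrase that allows either digit.

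If both muscles are used across the cohort, two things could follow. A constant gap unrelated to cardiac output adds spread to recovery time. That pulls the correlation towards zero and makes the regression slope less precise, although it does not shift the slope on average. If instead the choice of site goes with cardiac output, the gap acts as a confounder, and an unrecorded confounder cannot be adjusted for. The age correlation is exposed in the same way. So is the ratio at extubation, which bears on the secondary endpoint of residual weakness.

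**Working it through.** **Inputs from the documents.** N = 50, correlation 0.6 or greater, power above 90%, alpha 0.05 (section 10.1); two-sided tests (10.2); readings every 20 s (9.2), with form 18.2 running to +300 s. The negative sign used below follows the background in 4.2, where lower cardiac output goes with slower recovery.

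**Inputs that are assumptions.** The documents give no between-muscle gap *d*, no within-muscle SD *s*, no site mix *p* and no link between site and cardiac output. The ranges are *d* = 20, 40 or 60 s (one to three readings), *s* = 40 or 60 s, and *p* = 0.5, which gives the largest attenuation.

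**Step 1, the plan's own figure.** Power = Φ(atanh(r)·√(n−3) − 1.96) = Φ(0.693 × 6.856 − 1.96) = Φ(2.79) = 99.7%. A simulation of 40,000 runs also gives 99.7%, and Spearman with a variance factor of 1.06 gives 99.6%. The stated power above 90% is correct: 25 patients would give 90%, and 50 patients keep 90% power down to a correlation of 0.44.

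**Step 2, attenuation when site is unrelated to cardiac output.** r_pooled = r / √(1 + p(1−p)(d/s)²). With p = 0.5 this is −0.6 / √(1 + (d/2)²/s²).

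| s | d | (d/2)²/s² | r_pooled | Power, N = 50 |
|---|---|---|---|---|
| 60 s | 20 s | 0.028 | −0.59 | 99.7% |
| 60 s | 40 s | 0.111 | −0.57 | 99.3% |
| 60 s | 60 s | 0.250 | −0.54 | 98.4% |
| 40 s | 20 s | 0.063 | −0.58 | 99.5% |
| 40 s | 40 s | 0.250 | −0.54 | 98.4% |
| 40 s | 60 s | 0.563 | −0.48 | 94.8% |

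With an uneven mix the loss is smaller: at p = 0.2, a gap of 1 SD gives 0.6/√1.16 = 0.56 and power 99.1%. Power falls below 90% only with a gap of about 2 SD and an equal split: 0.6/√2 = 0.42, power 87.4%.

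**Step 3, hypothetical bias with no true correlation.** If site correlates 0.3 with cardiac output, d = 60 s, s = 60 s and p = 0.5, the spurious correlation has size 0.3 × 30 / √(60² + 30²) = 9/67.1 = 0.13. Its sign depends on which way the choice runs.

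Stated instead as a difference *e* in mean cardiac output between the site groups, with *e* and the recovery gap *g* both in SDs, r = 0.25·e·g / √((1 + 0.25e²)(1 + 0.25g²)). The two-sided rejection rate, nominally 5%, is then:

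- e = 0.5, g = 0.5: r = 0.06, about 7%
- e = 0.5, g = 1: r = 0.11, about 12%
- e = 1, g = 1: r = 0.20, about 28%

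**Step 4, cost of adjusting.** With the muscle as one covariate, power at a partial correlation of 0.6 is Φ(0.693 × √46 − 1.96) = Φ(2.74) = 99.7%, so adjustment costs almost nothing.

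**The case against.** The best reply is that 9.2 is poorly worded rather than open. Its one named target points to the little finger, and the discretion over location may mean the arm, which is what form 18.2 records. That reading is possible, so the documents do not establish that muscles will be mixed. It does not dispose of the point: the bullet separately allows either digit or both, and nothing on the form would show which was used.

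A reader might infer that the site can never be recovered. The documents do not support that. Section 8.1 says all intraoperative data are downloaded, and its list of flagged events is open-ended. The list in 6.6 is not stated to be complete, and nothing says that form 18.2 is the whole REDCap form. The figure in 19.1 was not available for this review and may or may not show electrode placement. What stands is that no listed source names the muscle.

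A reader might also infer that a patient monitored at both sites yields two outcomes. The form has one series and one recovery row, so the gap is only which site's reading is entered.

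On bias, nothing in the documents links site choice to cardiac output. Section 7.2 excludes surgery with an arm or leg in the sterile field and unilateral disorders such as carpal tunnel syndrome. Section 4.2 says EMG is unaffected by movement restricted by positioning. Both narrow the reasons for site choice to vary with patient factors. The bias scenario is therefore hypothetical.

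**Conclusion.** The point holds as a gap in the definition and capture of the primary measurement. Following 9.2 as written can put different muscles into one outcome, and the plan provides no documented means to detect or adjust for this.

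The size of any effect is unknown. Under the assumed gaps and SDs with an equal split, a true correlation of −0.6 would be observed as −0.59 to −0.48. It would be tempting to conclude that the study loses its power. It does not: power stays at about 95% or more across that range, and the sample-size statement stands. The likelier costs are an understated correlation and a slope that belongs to no defined muscle. A spurious correlation of about 0.13 needs a 60 s gap, a 60 s SD, an equal split and a site–cardiac output correlation of 0.3, none of which the documents supply.

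**What to change.** - In 9.2, correct the name of the target and state one default hand muscle for the primary endpoint in all patients where feasible. The choice of arm can stay with the anesthesiologist.
- On form 18.2, add a field for the muscle monitored, and state which site's reading counts if both are used.
- In 10.2, add one sensitivity analysis that repeats the primary correlation excluding, or adjusting for, patients monitored at the other muscle.

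The cost is a minor amendment, which under section 14 goes to the IRB, one form field and one extra analysis. The anesthesiologist has less freedom over site, and no added procedure is needed. It is best done before data are collected, because the site is simple to record at the time and may be hard to reconstruct later.

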10.1 Sample Size Determination

Based on Pearson correlation test, 50 patients will allow us to detect the correlation of 0,6 or greater between cardiac output and the time of recovery after reversal with sugammadex with a power greater than 90% and a significance level of 0.05.

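### The pre-blocker baseline TOFR is recorded but never used; adjusting the raw recovery time for it is a nearly free improvement, not the correction of an error

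*Combined protocol and SAP*

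**What the plan says.** Section 6.4 sets the primary endpoint as "the correlation between cardiac output and the time of recovery after reversal with sugammadex as measured by TOFR ≥ 0.9". Section 9.2 ends the timed readings on the same raw value: "After sugammadex administration, measurements will be taken every 20 seconds until consecutive measurements demonstrate a TOFR ≥ 0.9 (adequate recovery"). The outcome line of the form in 18.2 repeats it: "Time to recovery following SGX (TOFR ≥ 0.9) (two consecutive measurements"). The three places agree.

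A baseline is also collected. Section 9.2 states: "Following induction of anesthesia but prior to NMBA administration, baseline values will be recorded after calibration". The form in 18.2 has a row labelled "Calibrated baseline and supramax current" in a table whose columns are headed TOFC/TOFR #1 to #3. The text of 9.2 does not name TOFR. That a baseline TOFR can be entered, with up to three readings, is read from the layout of the form.

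Section 10.2 plans a Pearson or Spearman correlation of recovery time with cardiac output and with age, and a linear regression on either. It has no baseline term. No section divides later readings by the baseline or sets a minimum acceptable baseline.

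**The concern.** The primary result is a between-patient correlation. Anything that moves a patient's time to threshold for reasons other than cardiac output becomes outcome noise and pulls that correlation towards zero. A raw TOFR of 0.9 is 0.9/0.95 = 95% of full recovery for a patient whose unblocked TOFR is 0.95, and 0.9/1.05 = 86% for one at 1.05. The threshold lies near the plateau, where TOFR may rise slowly, so a small baseline difference can become a noticeable time difference. Section 9.2 also leaves the electrode site (thumb and/or little finger) to the anesthesiologist, which is a possible source of baseline spread.

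The information that could remove part of this noise is already on the form. At stake are the size of the estimated correlation and the precision of the slope. In an extreme case, a patient might have no recovery time at all.

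**Working it through.** **1. The plan's own figure.** Section 10.1 says "50 patients will allow us to detect the correlation of 0,6 or greater" with power above 90%; section 10.2 makes the test two-sided at 0.05. By Fisher's z, power = Φ(atanh(r)·√(n − 3) − 1.96). With r = 0.6 and n = 50: 0.693 × 6.856 − 1.96 = 2.79, so power is 99.7%. A simulation of the Pearson test (20,000 runs) also gives 99.7%. The stated figure is correct, and 25 patients would give 90%.

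**2. Effect of baseline on one patient's time (assumed curve).** Let TOFR rise exponentially to the patient's own plateau B. The approach phase to raw 0.9, relative to B = 1.00, is −ln(1 − 0.9/B)/ln 10.
- B = 0.95: 2.944/2.303 = 1.28, or 28% longer.
- B = 1.05: 1.946/2.303 = 0.85, or 15% shorter.

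**3. Effect on the correlation.** The documents give no baseline mean or SD, no recovery-time SD and no curve shape, so these are assumptions: B normal with mean 1.00 and SD 0.02 to 0.05, and a true correlation of −0.60 with normalised time (time to 0.9 × B). Each simulation used 400,000 patients. The exponential curve had mean time 150 s, SD 40 or 60 s and a 20 s grid. The sigmoid curve had Hill slope 3 or 5 and log-SD 0.3 or 0.5.

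| Baseline SD | r with raw time, exponential | r with raw time, sigmoid | Share with B < 0.9 |
|---|---|---|---|
| 0.02 | −0.59 | −0.58 to −0.60 | about 3 in 10 million |
| 0.03 | −0.56 to −0.58 | −0.56 to −0.595 | 0.04% |
| 0.05 | −0.49 to −0.54 | −0.49 to −0.58 | 2.3% |

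The last column is Φ(−0.1/SD). At SD 0.05 it is Φ(−2) = 2.3%, and 50 × 0.023 is about 1 patient.

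**4. Noise share and power.** If a share f of the outcome variance is baseline noise, r observed = 0.6·√(1 − f).
- r = 0.59: f = 1 − (0.59/0.6)² = 3%.
- r = 0.49: f = 1 − (0.49/0.6)² = 33%. Power = Φ(0.536 × 6.856 − 1.96) = Φ(1.715) = 95.7%.
- r = 0.44: f = 46%, power 89.9%. Only about here does power fall below 90%.

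**5. The slope.** Noise in the outcome does not attenuate a regression slope; the simulated ratio of raw to normalised slope was 0.99 to 1.05. It does widen the standard error. With the slope unchanged and the normalised variance set to 1, the raw variance is (0.6/r)² and the residual variance is (0.6/r)² − 0.36, against 0.64.
- r = 0.59: √(0.674/0.64) = 1.03, or 3% wider.
- r = 0.49: √(1.139/0.64) = 1.33, or 33% wider.

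**6. What adjustment recovers.** In the exponential model, adjusting raw time for B brings the correlation back to about −0.56 to −0.59. When the share of recovery time spent in the approach phase is varied from 50% to 100%, it comes back to −0.52 to −0.59.

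**7. Harsher assumptions.** If the whole recovery time is approach phase, SD 0.05 gives r as low as −0.42 (power 86.6%). A mean baseline of 0.95 with SD 0.05 gives −0.41 to −0.56 on the sigmoid curve, with about 8 of 50 patients below 0.9. The documents neither support nor exclude these cases.

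**The case against.** The strongest reply is that raw 0.9 is a declared choice. It is defined in the same way in 6.4, 9.2 and 18.2, section 9.2 labels it adequate recovery, and it is the endpoint that section 4.2 reports for the earlier studies this trial follows up. A normalised time is a different estimand, and keeping raw 0.9 preserves comparability. This stands, and the point does not ask for the definition to change.

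Second, the planned 0.6 refers to recovery time as section 6.4 defines it, that is, on the raw scale (section 10.1: "detect the correlation of 0,6 or greater between cardiac output and the time of recovery"). On that reading any baseline noise is already inside the planned effect. This also stands. The loss in the working is measured against a correlation with normalised time, which the plan never specifies, so it shows what adjustment could gain and not a shortfall in the plan.

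Third, every input on baseline spread is assumed, and at SD 0.02 the effect is negligible. The baseline row may also exist mainly for calibration, since it records the stimulation current too. Both are true. They limit the size of the point but give no reason to leave a recorded prognostic value out of the model.

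**Conclusion.** This is an improvement at almost no cost, not an error. The threshold is raw, a baseline is recorded, and the analysis does not use it. Under the assumed mean of 1.00 and SD of 0.02 to 0.05, the correlation would move from −0.60 to between about −0.59 and −0.49, and the slope's standard error would widen by 3% to 33%.

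A reader might infer more than the documents support:
- **That the trial is underpowered.** Power is 95.7% even at r = 0.49. It falls below 90% only if baseline noise takes nearly half of the outcome variance, which needs the harsher assumptions of step 7.
- **That the slope is biased towards zero.** Outcome noise costs precision only.
- **That some patients can never recover.** This needs a baseline below 0.9 and also a TOFR after reversal that does not exceed it. A baseline below 0.9 is expected in about 1 of 50 patients only at the top of the assumed range, and the documents show no such patient. How a patient who never reaches the threshold is analysed is a separate gap, whatever the baseline.
- **That the age analysis is biased.** This would need baseline TOFR to vary with age, on which the documents are silent.

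**What to change.** Keep raw TOFR ≥ 0.9 as the primary definition and leave the rule for ending the readings in 9.2 unchanged. In 10.2, before the data are examined, add:
1. A linear regression of raw recovery time on cardiac output, and one on age, each with the mean of the patient's recorded baseline TOFR readings as a covariate. If recovery time is log-transformed under 10.2, use the same scale here.
2. The matching partial correlation, reported beside the unadjusted correlation, which stays primary.
3. As a sensitivity analysis, time to 0.9 × baseline where the recorded readings allow it, with a count of the patients in whom it cannot be determined. These will be patients with a baseline above 1.0 whose readings ended before their own criterion was met.

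Section 9.2 or the form should also state that the baseline entry is a TOFR.

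The cost is a few lines of text and one degree of freedom; no new measurement is needed. The gain is smaller if baseline readings are noisy or vary little. The covariate cannot supply a recovery time for a patient who has none. Specifying the adjustment now avoids the charge that it was chosen after seeing the result.
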